**Impact of a Virtual Diabetes Self-Care and Education Program
on Diabetes-related Outcomes in Latinos with T2 Diabetes**

NCT02488785

Document date Oct 27/2015

PROGRAM DESCRIPTION/PLAN OF OPERATION

PURPOSE OF PROTOCOL:

The goal of this study is to evaluate the impact of a comprehensive diabetes education and management program based on frequent communication with patients using teleconsultation, text messaging, and phone calls on diabetes related outcomes in Latino patients with type 2 diabetes. We hypothesize that the decline in hemoglobin A1c value between the baseline and the six-month visit will be at least 0.5 percent greater in the intervention group than in the control group.

1. Objectives:

- a. Improve adherence to nutritional therapy, physical activity, glucose monitoring and medication use in Latino patients with type 2 diabetes by using a virtual diabetes education and self-management program in a six month period and in comparison to usual diabetes care and education received in diabetes clinics.
- b. Improve A1c levels, blood pressure, lipids and weight control in Latino patients with diabetes using this program within the same time frame.
- c. Improve adherence to clinic appointments and decrease diabetes related stress, depression, visits to the emergency room and hospitalizations with the use of this program in comparison to people receiving usual diabetes care.
- d. Evaluate the impact of each of the three components of the program (teleconsultations, text messaging and phone calls) on the adherence to basic diabetes self-care behaviors.

2. Activities:

Setting:

Joslin Affiliated Center at Doctor's Hospital at Renaissance in Edinburg (DHR), TX.

Duration:

18 months total:

1. 3 months for IRB approval and training at the partner site
2. 12 months of continuous enrollment (including 9 months of study)
3. 3 months of data analysis and manuscript preparation

Protocol:

Inclusion Criteria:

In order to participate in the program, all patients must meet the following criteria:

1. Have physician-diagnosed type 2 diabetes
2. Be self-identified as Hispanic or Latino
3. Age 21 to 80
4. An A1c value between 8-14% within the last three months.
5. Demonstrate the ability, either alone or with the help of a family member that will be with the patient at least once a week, to use the technology that will be used during the teleconsultations.

Exclusion Criteria:

Subjects will be excluded if they have any of the following conditions:

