1. Severe diabetes related chronic complications such as chronic renal failure, blindness, amputations, stroke, etc.
2. Concomitant chronic illnesses that would affect their participation in the program, i.e. cancer, debilitating diseases, etc.
3. Any other condition that would affect participant's basic mental health skills.
4. Type 1 diabetes or gestational diabetes.
5. Patients with abnormal hemoglobin, anemia or any condition that may affect red blood cell turnover. Any of these conditions may be detected through participants' history or through the laboratory report at study screening.
6. Signs or symptoms of metabolic decompensation (polyuria, polydypsia, polyphagia, unexplained weight loss, blurry vision, lethargy, etc.)

Elimination Criteria:

Development of any acute event during the study period that would affect participants' primary outcome at the discretion of the investigator, e.g. hyperosmolar coma, acute event of significant hyperglycemia or the use of certain medications like steroids.

Groups:

A total of 92 participants will be randomly assigned to one of the two study groups:

Group 1 – Intervention group – this group will complete activities described above. During scheduled follow-up clinical visits at months 3, 6, and 9, an additional A1c will be obtained. All measurements will be covered through the study grant if the patient does not have a recent laboratory result (2 weeks prior to the study visit) for the following test: A1c, lipid panel, ALT, AST, microalbumin, and chem 6 result.

Group 2 - Control Group –

This group will attend regular visits with their medical and education providers. As in the intervention group, these visits are expected to occur at 3, 6, and 9 months after the first visit. This group corresponds to the usual care that is provided at DHR.

Primary Outcome:

The primary outcome variable will be the change in hemoglobin A1c value from baseline to 6 months.

Sample Size:

We hypothesize that the decline in hemoglobin A1c value between the baseline and the six-month visit will be at least 0.5 percent greater in the intervention group than in the control group.

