The sample size and power calculation is based on preliminary results of our study where the study aimed at behavioral change. Assuming a mean reduction of 0.504 (SD= 1.2) in A1c in the intervention group and no change in the control group a sample size of 37 per group will be needed to detect this reduction with 80 % at 5% level of significance (one-sided) using the t-test. Assuming a 20% dropout, 46 study subjects per group (total 92) will be needed.

Recruitment:

Study Protocol

Study candidates will be identified at the partner site (DHR) where this protocol will take place. This will be done by creating flyers, videos, print and web-based ads, and letters to invite patients that attend the practice to join the study and/or by directly inviting patients that regularly attend the practice. Proper informed written consent will be obtained from all individuals prior to participation in the study.

Interventions:

a. Virtual diabetes self-management group

- i. Weekly conversations led by the diabetes educator (30-minute) using teleconsultation to deliver diabetes education and enhance adherence to treatment recommendations. These conversations will occur during the first 12 weeks of the intervention and will consist of the following elements: a) open question as to whether there is a particular item for discussion that the patient would like to address; b) review of blood glucose and physical activity results; c) review of the adherence to the four basic self-care behaviors (meal plan, physical activity, glucose monitoring and medications); d) identification of barriers to adhere to treatment recommendations; and e) provision of specific recommendations to overcome identified barriers. In order to provide diabetes education in a culturally and linguistically oriented manner, particularly to those patients with low health literacy, all participants in the virtual education program will be encouraged to listen to Rosa's or Jose's Story during the first 8 weeks of the intervention. These are audio-novellas developed by the Latino Diabetes Initiative at Joslin Diabetes Center to educate Latino patients with type 2 diabetes using the story telling method in a practical and engaging manner.

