- ii. Since the teleconsultations will only last 12 weeks, phone conversations with the diabetes educator will be implemented starting in the 4th month of the program. These will be 15-30 minute conversations and will occur at weeks 14, 15, 16, 17, 19, 21, and 23. The goal of the phone calls is to provide support to the patients and they will follow the same protocol as the weekly conversations described above.
- iii. A weekly text message will be sent to patients during the 6 months of the education program. These messages will focus on assessing and addressing participants' beliefs about common myths and misconceptions in the area of diabetes. The text message will present the myth of the week and request people's participation in responding whether the concept is true or false and will also provide the correct answer to the question presented the prior week.
- iv. Observation period: the third quarter of the intervention (months 6-9) will allow the observation of the residual effect of the virtual education program; therefore no contact or education will be planned for the last 3 months (months 7, 8 & 9). Patients will be followed in their corresponding clinics as usual.

b. In-person diabetes self-management education or control group

- i. Patients in this group will attend their regular clinical and education appointments as offered by the center.

The table below presents the timeline for the interventions discussed above.

	Months								
	1	2	3	4	5	6	7	8	9
Virtual education	4w R/J 4T	4w R/J 4T	4w 4T	4p 4T	2p 4T	1p 4T			

W=weekly teleconsultation

P=Phone conversation

R/J=Rosa or Jose's Story

T=Text message related to a diabetes myths and misconceptions

Study Procedures:

Before randomization, all participants will go through the following steps:

- 1) Eligible patients will have their standard follow-up clinical encounter with their corresponding health care provider.
- 2) Screening visit. At this time, the research assistant or study coordinator will obtain the baseline A1c measured through each site's laboratory and will review inclusion and exclusion criteria with study candidates to assess eligibility for the study. If the patient qualifies for the study, clinicians will not be aware of this at the time of the initial visit, so that this value does not influence their treatment at baseline and the intervention is left as the main explanatory variable.

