After the regular clinical visit and the screening visit the eligible participants will be randomized to one of the two groups.

After randomization, participants will go through the following steps:

- 3) All participants in the study will receive a healthy eating handout, pedometer with exercise handout, and pillbox and will be invited to come to the center for an initial 2-hour nutrition and exercise recommendation group session taught by the diabetes educator. The research assistant and/or study coordinator will provide these items and book to patients that want to participate in the group session.
- 4) Participants in the intervention group will receive education and training on how to operate the technology as well as copies of Rosa's or Jose's Story in their preferred language and based on their education needs. A calendar with specific dates and times for their weekly/monthly interaction with the diabetes team will be provided to participants.

Study Protocol

- 5) All study participants will be given a follow-up appointment 3, 6, and 9 months after the baseline visit.

Project related materials:

Patient Education:

At baseline, all patients in the study will have the opportunity to come to the center for initial 2-hour nutrition and exercise recommendation group session. They will receive handouts regarding food, exercise, medication and will emphasize the need to take medications and insulin on time, follow meal plans, be physically active and monitor blood glucose levels as recommended by their health care provider. This information will be available in English and Spanish and will be based on culturally oriented materials for Latino patients with low/medium health literacy.

Resources for Providers:

All providers will receive training and log-in information for the teleconsultation.

The partner site will receive ***Patient Education Handouts*** (in English and Spanish) that providers can use whenever necessary to support changes to treatment plans for study participants. For instance, handouts on how to start and advance insulin therapy will be provided. Information on other pharmacologic interventions will also be available. Providers will have access to the electronic versions of all handouts

Patient Incentives:

Each participant will receive \$35 every time they complete a study visit. Participants will be asked to complete four study visits in a period of nine months.

Study Visits:

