Before any study procedure is done, the patient will be asked to read the consent form. A member of the study staff will discuss the study and the study procedures. Additional time from participants' regular clinical appointments will be necessary to collect study related information as follows:

Visit 1: This visit will last 60 minutes and will start by obtaining an A1c value to verify patient's eligibility. After a patient has been enrolled in the study (A1c value between 8-14%) they will be randomly assigned to the control or intervention group (virtual diabetes self-management education program using teleconsultation) and baseline information will be collected. Participants in the intervention group will be trained to use technology related to the teleconsultation, their own glucometer and the pedometer administered by this program.

Visit 2: This visit will last 60 minutes for questionnaires and will be completed 3 months after visit 1. All the tests and questionnaires detailed in table 1 will be administered at this visit.

Visit 3: This visit will last 60 minutes for questionnaires and will be completed 6 months after visit 1. All the tests and questionnaires detailed in table 1 will be administered at this visit.

Study Protocol

Visit 4: This visit will last 60 minutes for questionnaires and will be completed 9 months after visit 1. All the tests and questionnaires detailed in table 1 will be administered at this visit.

Timeline Table for Study Procedures:

Study Variables (both groups)	Baseline Visit	3	6	9
Laboratories				
Blood drawn	x	x	x	x
A1c	x	x	x	x
Lipid profile	x	x	x	x
ALT (from patient record if available)	x	x		x
AST (from patient record if available)	x	x		x
Microalbumin (from patient record if available)	x		x	x
Chem 6 (from patient record if available)	x	x		x
Measurements				
Weight	x	x	x	x
Height	x			
Blood pressure	x	x	x	x
Questionnaires				
Demographic characteristics	x			
Diabetes history	x			
Diabetes treatment plan	x	x	x	x
Adherence to prescribed drugs	x	x	x	x
Measures of emotional distress (depression, anxiety and PAID)	x		x	
Health literacy	x			
Self-care behaviors	x	x	x	x
Executive function	x			
Depression scale	x	x	x	x
Physical activity: pedometer use and number of steps per day	x	x	x	x
24 hour recall	x	x	x	x
Food frequency questionnaire	x	x	x	x
Analysis of the photo of the content of the refrigerator (only for the intervention group)	x	x	x	x

IRB:

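### The only test named for the primary outcome is an unadjusted t-test; ANCOVA on the pre-randomisation A1c should be named as the primary analysis, at almost no cost and for a gain of unknown size

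*Combined protocol and SAP*

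**What the plan says.** The Primary Outcome section states: "The primary outcome variable will be the change in hemoglobin A1c value from baseline to 6 months". The Sample Size section hypothesises a decline "at least 0.5 percent greater in the intervention group than in the control group" and sizes the trial thus: "Assuming a mean reduction of 0.504 (SD= 1.2) in A1c in the intervention group and no change in the control group", giving 37 per group for 80% power at a 5% "level of significance (one-sided) using the t-test". That t-test is the basis of a power calculation and is not declared as the analysis. No other test, model or covariate is named for the primary outcome anywhere in the combined protocol and SAP.

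Baseline A1c comes before allocation. At the screening visit (Study Procedures, steps before randomisation) "the research assistant or study coordinator will obtain the baseline A1c", and then: "After the regular clinical visit and the screening visit the eligible participants will be randomized to one of the two groups". Under Study Visits, Visit 1 has the same order: "After a patient has been enrolled in the study (A1c value between 8-14%) they will be randomly assigned". The section on process and product study variables says that the baseline value determines eligibility, so every randomised participant should have one.

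**The concern.** A t-test on the change score fixes the slope of 6-month A1c on baseline A1c at 1. ANCOVA estimates that slope. When the true slope is not 1, the change-score test carries avoidable variance. The covariate here is measured before randomisation, is available for everyone and is the same variable as the outcome.

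Precision is at stake, not bias. It matters because the trial is small and, on its own inputs, short of power. In addition, with no declared analysis, the choice between adjusted and unadjusted models could be made after the data are seen.

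**Working it through.** **Inputs from the Sample Size section.** Difference 0.504; SD 1.2, read as the SD of change and common to both groups; 37 evaluable per group; one-sided 5%; 80% power.

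**Inputs not in the documents (assumed).** r, the correlation of baseline and 6-month A1c: 0.3, 0.5, 0.7, 0.8. k, the ratio of 6-month SD to baseline SD: 0.8, 1, 1.25.

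**Step 1: the plan's own figure.** For two groups, n = 2 × [1.2 × (1.645 + 0.842) / 0.504]² ≈ 70.1, so 71 per group; the exact noncentral t also gives 71. The stated 37 does not reproduce for a between-group test. A one-sample or paired t-test with the same inputs gives exactly 37 (power 80.5%). At 37 per group the two-sample test has:
- SE = 1.2 × √(2/37) = 0.279
- noncentrality = 0.504 / 0.279 = 1.81 on 72 df, so power 55.7%
- two-sided 90% CI half-width = 1.67 × 0.279 = 0.47

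**Step 2: variance under ANCOVA.** Write SD0 for the baseline SD.
- Var(change) = SD0² (1 + k² − 2rk) = 1.2² = 1.44
- ANCOVA residual variance = SD0² k² (1 − r²)
- Ratio = k² (1 − r²) / (1 + k² − 2rk)
- 1 − ratio = (1 − rk)² / (1 + k² − 2rk), which is never negative

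The ANCOVA residual variance therefore never exceeds the change-score variance. The two are equal only when rk = 1, that is, when the slope is 1. With k = 1 the ratio simplifies to (1 + r)/2.

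**Step 3: power at 37 per group.** Residual SD = 1.2 × √ratio; noncentral t on 71 df. Example, k = 1 and r = 0.5: ratio 0.75, residual SD 1.039, SE = 1.039 × √(2/37) = 0.242, power 66.3%, and 54 per group for 80%.

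| k | r | Variance ratio | SE | Power at 37 per group | n per group for 80% | Implied baseline SD |
|---|---|---|---|---|---|---|
| t-test | – | 1 | 0.279 | 55.7% | 71 | – |
| 1.25 | 0.3 | 0.784 | 0.247 | 64.6% | 56 | 0.89 |
| 1.25 | 0.5 | 0.893 | 0.264 | 59.8% | 64 | 1.05 |
| 1.25 | 0.7 | 0.981 | 0.276 | 56.4% | 70 | 1.33 |
| 1.25 | 0.8 | 1.000 | 0.279 | 55.7% | 71 | 1.60 |
| 1 | 0.3 | 0.650 | 0.225 | 71.7% | 47 | 1.01 |
| 1 | 0.5 | 0.750 | 0.242 | 66.3% | 54 | 1.20 |
| 1 | 0.7 | 0.850 | 0.257 | 61.6% | 61 | 1.55 |
| 1 | 0.8 | 0.900 | 0.265 | 59.5% | 64 | 1.90 |
| 0.8 | 0.3 | 0.502 | 0.198 | 81.1% | 36 | 1.11 |
| 0.8 | 0.5 | 0.571 | 0.211 | 76.5% | 41 | 1.31 |
| 0.8 | 0.7 | 0.628 | 0.221 | 73.0% | 45 | 1.66 |
| 0.8 | 0.8 | 0.640 | 0.223 | 72.3% | 46 | 2.00 |

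The 90% CI half-width runs from 0.33 to 0.47. One of the 12 cases reaches 80% power at 37 per group.

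**Step 4: cost of estimating the slope.** One degree of freedom (72 to 71) and expected variance inflation of 1 + 1/(2n − 4) = 1 + 1/70 = 1.014. Simulation that includes this (20,000 trials per case) gives, in the worst case (k = 1.25, r = 0.8), 54.8% for ANCOVA against 55.4% for the t-test, a loss of under 1 point. At k = 1, r = 0.5 ANCOVA has 66.2%.

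**The case against.** The strongest reply is that no error has been shown. The t-test is unbiased and was used only for planning, and sizing a trial on it does not bar an adjusted analysis later. That is right, and it makes this a recommendation. It does not remove the point, because no primary analysis is declared and one has to be named.

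The gain rests on r and k, which are assumed, and it may be zero. This also stands. The top of the range (k = 0.8) has no support in the documents. Eligibility requires "An A1c value between 8-14% within the last three months", while 6-month A1c is unrestricted. That could make the 6-month SD the larger one (k above 1), which reduces the gain, or lower the correlation, which increases it. For k of 1 the table gives gains of about 4 to 16 points, and for k = 1.25, 0 to 9.

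Two cells imply baseline SDs of 1.90 and 2.00, above the 6/√12 = 1.73 of a uniform spread over 8–14%, so they fit the eligibility limits poorly. Dropping them leaves the 0 to 25 point range unchanged.

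The algebra also assumes the same slope and SD in both groups. Simulations with unequal slopes at 37 per group changed the standard error by between about 11% lower and under 1% higher, so this objection does not hold.

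Finally, the 55.7% power and 71 per group arise from the sample-size error and should not be counted again here. That is accepted; they serve only as the reference for the comparison.

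**Conclusion.** The point holds as a recommended improvement. It is not a validity error. Adjusting for baseline A1c is expected to be at least as precise as the unadjusted change-score test, apart from a small-sample cost of under 1 power point. The gain is 0 to 25 points over the assumed grid, and its true size cannot be found from the documents. The figures rest on 1.2 being the SD of change and common to both groups, and on 37 evaluable participants per group. ANCOVA should not be offered as the remedy for the power shortfall: by the normal approximation, 80% power at 37 per group needs a variance ratio of about 37/70.1 = 0.53, which only one case in the grid meets.

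**What to change.** Add one sentence naming a single primary analysis: the between-group difference in 6-month A1c, estimated by ANCOVA with group and the baseline A1c measured before randomisation, with participants analysed in the group to which they were randomised. The estimand does not change, because with baseline in the model the group coefficient is the same for 6-month A1c and for change.

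Report a two-sided 90% confidence interval, which matches the one-sided 5% test. If a 95% interval is preferred, first restate the test as one-sided 2.5% (two-sided 5%). Power at 37 per group is then 43.0% for the t-test and, at k = 1, 59.9%, 53.9% and 48.9% for ANCOVA with r = 0.3, 0.5 and 0.7.

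The cost is the wording, one degree of freedom and about 1.4% expected variance inflation. No new data or visits are needed, and using the 3-month A1c is optional. Analysis as randomised has to be reconciled with the Elimination Criteria, and the 20% dropout still needs its own handling; this sentence settles neither.

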The Joslin Diabetes Center's Institutional Review Board will be in charge of approving this protocol according to current clinical research guidelines.

Study Protocol

An informed consent for participation in the study will be generated to be approved by the IRB. This consent form will be given to all participants before the study begins. Only participants that have given full written consent will be able to participate in the study.

Adverse Events:

We don't anticipate any serious adverse events as this is a study that does not involve the use of any major procedure or the use of any pharmacologic intervention. The only potential adverse events are those related with answering questionnaires or drawing blood for the A1c test and other laboratories specified above.

Good Clinical Practice:

Whereas the primary objective of the protocol is to assess whether there is a significant difference in glycemic control with teleconsultations with the diabetes team at the patient's home, all participants in the study regardless of the **assigned study** group will be offered the best possible diabetes care according to current standards and approved treatment algorithms, particularly the recently published American Diabetes Association standards.

If at any point in time during the study, the investigators or practicing clinicians consider that it would be in the patient's best interest to terminate their participation in the study; this will be considered a priority.

Process and product study variables:

Primary outcome:

- **A1c levels:**

The values obtained through the laboratory at each of the participating sites will be used to evaluate the primary outcome of the study. The baseline A1c value will be used for eligibility for the study.

Other variables:

- **Demographic characteristics** (obtained at baseline)

The demographic variables of interest are: date of birth, years in the practice, household status (living with one or more persons, living alone), years of education, socioeconomic status, community of residence and insurance status.

- **Diabetes history** (obtained at baseline)

The variables of interest are: date of diagnosis, age at diagnosis, years with diabetes, family history of diabetes, diabetes specialist care and history of diabetes education.

- **Diabetes treatment plan** (obtained at baseline and during each clinical encounter in both groups and during the teleconsultations and telephone communications in the intervention group)

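### The plan meets an expected 20% dropout only by enrolling more, and states no way to obtain the 6-month A1c of participants who stop attending

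*Combined protocol and SAP*

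**What the plan says.** The Primary Outcome section defines the endpoint: "The primary outcome variable will be the change in hemoglobin A1c value from baseline to 6 months". The A1c entry under Process and product study variables names its source: "The values obtained through the laboratory at each of the participating sites will be used to evaluate the primary outcome of the study". The Recruitment section includes "directly inviting patients that regularly attend the practice" among the ways of finding candidates.

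For dropout, the Sample Size section says "Assuming a 20% dropout, 46 study subjects per group (total 92) will be needed". It gives no other measure against the loss.

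The one clause on existing laboratory results stands under Group 1 in the Groups section. There the grant pays for tests, A1c among them, "if the patient does not have a recent laboratory result (2 weeks prior to the study visit"). The clause presupposes a study visit, and it is not repeated for the control group.

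The Timeline Table for Study Procedures marks ALT, AST, microalbumin and Chem 6 as obtainable from the patient's record. It does not mark A1c that way. The Study Visits section places data collection in extra time around regular clinic appointments. The document does not define dropout or a time window for the 6-month A1c. It gives no missing-data method and no procedure for obtaining an A1c once study visits have stopped.

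**The concern.** Dividing by one minus the dropout rate treats every dropout as a person with no primary outcome. That is a normal allowance for lost numbers, but it does nothing about who is lost. In this trial some of the loss may be avoidable. A participant can tire of the calls or of the 60-minute questionnaire session and still see the centre's clinicians, with an A1c measured in the laboratory that supplies the endpoint.

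The reasons for stopping can plausibly differ by arm. Only the intervention group has 12 teleconsultations and 7 phone calls, and objective c sets out to improve adherence to clinic appointments, so the programme is meant to change attendance itself. If those who stop in the intervention arm benefited less than those who stay, a comparison of attenders overstates the effect in everyone assigned to the programme. A larger enrolment would estimate the same biased quantity more precisely.

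This point concerns participants who stop of their own accord. Removal under the Elimination Criteria, or by clinicians, is a different question.

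**Working it through.** **Inputs.** From Sample Size: "Assuming a mean reduction of 0.504 (SD= 1.2) in A1c in the intervention group and no change in the control group". The same section gives 37 evaluable per arm, 80% power, a one-sided t-test at the 5% level, 20% dropout and 46 enrolled per arm. From Interventions: 12 weekly teleconsultations, then calls at weeks 14, 15, 16, 17, 19, 21 and 23, so 12 + 7 = 19 conversations. Not in the document, and therefore assumed over a range: the benefit in dropouts, and the share of dropouts with a usable A1c near month 6.

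**1. The plan's dropout step.** 37 / (1 − 0.20) = 46.25. The plan has 46 (rounding up would give 47), so this step reproduces and confirms that dropouts are counted as giving no outcome.

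**2. Number affected.** 0.20 × 46 = 9.2 per arm, about 18 of 92, leaving 36.8 per arm.

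**3. Possible bias.** Take the plan's 0.504 as the effect among attenders, let controls not change (the plan's own assumption), and let intervention dropouts gain a fraction b of 0.504. The effect in all randomised is 0.504 × (0.8 + 0.2b).

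| b | Attenders only | All randomised | Overstatement |
|---|---|---|---|
| 1 | 0.504 | 0.504 | 0% |
| 0.5 | 0.504 | 0.454 | 11% |
| 0 | 0.504 | 0.403 | 25% |

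**4. What partial recovery does to the bias.** In the extreme case (b = 0), suppose half the dropouts are recovered and resemble those not recovered. The estimate becomes 0.504 × 36.8 / 41.4 = 0.448. Against 0.403 that is still 11% too high. Recovery reduces the bias and removes it only if complete.

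**5. Precision.** SE of the difference = 1.2 × √(2/n), with SD 1.2 in each arm.
- n = 37 (none recovered): 0.279
- n = 41 (about half recovered): 0.265
- n = 46 (all recovered): 0.250

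**6. Power.** With difference 0.504, SD 1.2 and a one-sided 5% two-group t-test, power is 55.6% at 36.8 per arm, 59.9% at 41.4 and 63.8% at 46. These inputs need 71 per group for 80%, not 37; 37 is what a one-sample t-test gives (power 80.5%). That is a separate problem, and full recovery does not repair it.

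**The case against.** The strongest reply is that a gap is being read as a rule. A reader might infer that the plan discards the A1c of anyone who misses Visit 3. The document does not say so: the 2-week clause concerns who pays for a test, and the statement on the endpoint's source carries no attendance condition. A reader might equally infer that routine laboratory values already count as study data in both arms. That is not supported either, since the clause is tied to a study visit and written for Group 1 only. What stands is that retrieval is not provided for.

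Second, the recoverable share is unknown. Study visits are built around clinic appointments, so a participant who misses month 6 may have missed the clinic too. The yield could be anywhere from 0% to 100%. This stands, and it is a reason to offer a blood draw before relying on records.

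Third, 25% is the extreme of a range, not an estimate. It needs zero benefit in every intervention dropout, no change in controls, and an attenders-only analysis that the document does not specify. Participants who are doing well may also stop, and dropouts who gained more than attenders would reverse the direction. This stands.

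Fourth, a wide window would harm the endpoint. Months 7 to 9 are a period without programme contact, meant to show residual effect, and a value at month 8 lies closer to the 9-month visit than to month 6. This stands, and it limits the window that can be proposed.

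Finally, inflating enrolment by 20% is ordinary planning. That is true, but it addresses numbers and not selection.

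**Conclusion.** The concern holds as a design weakness that should be corrected: the plan expects to lose about 9 outcomes per arm and states no way to obtain any of them, in a setting where some may be obtainable. The possible overstatement in an attenders-only comparison is 0% to 25%, assuming 20% dropout, unchanged controls, and a benefit in intervention dropouts between all and none of that in attenders. The gain from retrieval is less missing data and less possible bias. The precision gain is small, from an SE of 0.279 to at best 0.250. It would be wrong to conclude that the plan refuses such values, that the effect will be overstated by 25%, or that retrieval restores 80% power.

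**What to change.** Add to the primary outcome definition, for both arms:

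- A participant who stops programme contacts or study visits, and has not withdrawn consent for record use, stays in outcome follow-up.
- If Visit 3 is missed, offer an A1c-only draw without the questionnaires.
- Failing that, use the site-laboratory A1c closest to 6 months within a pre-set window that stays nearer to month 6 than to the 3- or 9-month visit, for example 4.5 to 7.5 months (the midpoints), extracted by the same rule in both arms.
- Report the source of the values by arm, and add a sensitivity analysis on Visit 3 values only.

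The cost is a paragraph in the protocol, a record look-up for about 18 people, and a consent line on record use after visits stop, if the form lacks one (the consent pages are not available here). The sponsor should also decide whether the draw is paid, since the $35 is tied to completing a study visit and paying the same for less could encourage skipping the questionnaires.

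The downsides should be stated in the plan. The yield is unknown. Some values will be off-schedule by up to about 6 weeks, including some taken after programme contact ends. Patients with a routine test may differ from those without one.
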